2.8.1.4 AE summaries

The following adverse event summaries will be produced:

- Adverse events, regardless of study drug relationship by primary system organ class, preferred term and maximum CTC
- Adverse events with suspected relationship to study drug by primary system organ class, preferred term and maximum CTC
- Adverse events with an overall incidence rate of 5% or more in either treatment arm, regardless of study drug relationship by primary system organ class and preferred term
- CTC grade ≥ 3 adverse events, regardless of study drug relationship by primary system organ class and preferred term
- CTC grade ≥ 3 adverse events with suspected study drug relationship by primary system organ class and preferred term
- Deaths, by primary system organ class and preferred term
- On-treatment deaths, by primary system organ class and preferred term
- Serious adverse events, regardless of study drug relationship, by primary system organ class and preferred term
- Serious adverse events with suspected study drug relationship, by primary system organ class and preferred term
- Serious adverse events with fatal outcome
- Non-Serious AEs (threshold $\geq 5\%$), regardless of study drug relationship, by primary system organ class and preferred term
- Adverse events leading to study drug discontinuation, regardless of study drug relationship, by primary system organ class and preferred term
- Adverse events leading to study drug discontinuation, with suspected study drug relationship, by primary system organ class and preferred term
- Adverse events requiring dose adjustment or study-drug interruption, regardless of study drug relationship, by primary system organ class and preferred term

- Adverse events requiring additional therapy, regardless of study drug relationship, by grade, primary system organ class and preferred term

For the legal requirements of ClinicalTrials.gov and EudraCT, two required tables on on-treatment adverse events which are not serious adverse events with an incidence greater than 5% and on on-treatment serious adverse events and SAE suspected to be related to study treatment will be provided by system organ class and preferred term on the safety set population.

If for the same patient, several consecutive AEs (irrespective of study treatment causality, seriousness and severity) occurred with the same SOC and PT:

- a single occurrence will be counted if there is ≤ 1 day gap between the end date of the preceding AE and the start date of the consecutive AE
- more than one occurrence will be counted if there is > 1 day gap between the end date of the preceding AE and the start date of the consecutive AE

For occurrence, the presence of at least one SAE / SAE suspected to be related to study treatment / non SAE has to be checked in a block e.g., among AE's in a ≤ 1 day gap block, if at least one SAE is occurring, then one occurrence is calculated for that SAE.

The number of deaths resulting from SAEs suspected to be related to study treatment and SAEs irrespective of study treatment relationship will be provided by SOC and PT.

2.8.1.5 Adverse events of special interest / grouping of AEs

An adverse event of special interest is a grouping of adverse events that are of scientific and medical concern specific to compound everolimus. These groupings are defined using MedDRA terms, SMQs (standardized MedDRA queries), HLTs (high level group terms), HLT (high level terms) and PTs (preferred terms). Customized SMQs (Novartis MedDRA queries, NMQ) may also be used. A NMQ is a customized group of search terms which defines a medical concept for which there is no official SMQ available or the available SMQ does not completely fit the need. It may include a combination of single terms and/or an existing SMQ, narrow or broad. For each specified AESI, number and percentage of subjects with at least one event of the AESI occurring during on treatment period will be summarized by treatment arm. Time to first occurrence of AESI by variable was provided in the primary CSR (DCO: 05-May-2020) and hence will not be repeated in the report. The updated information will be provided in the listings.

A Case Retrieval Sheet (CRS) with the exact composition of the AE groupings is to be used to map reported AEs to the AESI groupings. This file may be updated (i.e. it is a living document) based on review of accumulating trial data, and therefore the groupings are also subject to potential change. Table 2-3 provides the latest groupings at the time of the finalization of the SAP. The most up-to-date version of the CRS will be used at the time of the analysis.

Table 2-3 AESI groupings

AESI grouping	MedDRA category
Wound healing complications	CMQ

Thrombotic and embolic events	CMQ
Stomatitis	CMQ
Severe infections	SOC
Pre-existing infection (reactivation, aggravation, or exacerbation)	CMQ
Muscle wasting / Muscle loss	CMQ
Renal failure	CMQ
Hypophosphatemia	SMQ
Hyperglycemia/ new onset of diabetes mellitus	SMQ
Haemorrhages	SMQ
Dyslipidemia	SMQ
Cytopenia	CMQ
Cardiac failure	SMQ
Hypersensitivity (anaphylactic reactions)	SMQ
Non infectious pneumonitis	SMQ

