1.1 Study design

This is a multicenter, double-blind, randomized, placebo-controlled, phase II study evaluating treatment with everolimus (10 mg daily) versus placebo in combination with exemestane (25 mg daily) in Chinese postmenopausal women with locally advanced, recurrent or metastatic ER positive HER2-negative breast cancer refractory to non-steroidal aromatase inhibitors.

Approximately 160 subjects will be randomized in 1:1 ratio to receive either everolimus or matching placebo in a blinded manner in addition to open label exemestane (25 mg daily tablets).

All eligible subjects will be randomized within 7 days before Cycle 1 Day 1 to one of the two treatment arms: everolimus plus exemestane arm or placebo plus exemestane arm. Randomization will be stratified according to the presence of visceral disease and sensitivity to prior hormonal therapy status. Visceral refers to lung, liver, brain, pleural and peritoneal involvement.

Randomized subjects will start the study treatment at Cycle 1 Day 1. Subjects will receive everolimus/placebo (10 mg daily oral tablets) in addition to exemestane (25 mg daily oral tablets) continuously.

Subjects will receive treatment until disease progression (assessed by RECIST 1.1), unacceptable toxicity, death or discontinuation from treatment for any other reason. Tumor assessments will be performed every 8 weeks after randomization until radiological progression per local assessment.

There won't be any interim analysis for this study.

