1.2 Study objectives and endpoints

The primary objective is to assess the progression-free survival (PFS) as determined by investigator assessment of everolimus plus exemestane and of placebo plus exemestane.

The secondary objectives are:

- To assess PFS in the two treatment arms as determined by a Blinded Independent Review Committee (BIRC)

- To assess overall survival (OS) in the two treatment arms
- To assess the following efficacy endpoints in the two treatment arms based on both local investigator's assessment and BIRC
 - Overall response rate (ORR)
 - Clinical benefit rate (CBR)
 - Time to response and duration of response
- To assess time to deterioration of ECOG Performance Status (PS)
- To characterize the safety and tolerability of everolimus and exemestane versus placebo and exemestane
- Characterize the pharmacokinetics of everolimus pre-dose concentration (C_{min}) and concentration at 2 hours post dose (C_{2h}) when administered in combination with exemestane
- Compare the two treatment arms with respect to pre-dose concentration (C_{min}) and concentration at 2 hours post dose (C_{2h}) of exemestane and to compare the two treatment arms with respect to estradiol (E2) changes from baseline.

For secondary objectives with regards to BIRC assessment and PK analyses, the analysis will not be repeated for the final CSR as per protocol. The results were addressed in the primary CSR (DCO:19-May-2020).

2 Statistical methods

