2.1.5 Date of last administration of study treatment

The date of last administration of study treatment is defined as the last date when a non-zero dose of any component of study treatment was administered and recorded on the DAR eCRF.

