2.1.8 On-treatment assessment/event

On-treatment assessment/event is defined as any assessment/event obtained in the time interval:[date of first administration of study treatment; date of last administration of study treatment + 30 days], i.e., including the lower and upper limits. (Note: The calculation of study treatment duration, however, may use different rules as specified in [Section 2.4.1](#).)

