2.8.1.3 General rules for AE Reporting

AE summaries will include all AEs starting on or after study day 1 (i.e., on or after the day of the first intake of study treatment) and starting no later than 30 days after the last treatment/exposure date. All AEs, deaths and serious adverse events will be listed. AEs starting prior to study day 1 and AEs starting later than 30 days after the last treatment/exposure date will be flagged in the listings.

AEs will be summarized by presenting the number and percentage of subjects having at least one AE and having at least one AE in each body system/primary system organ class, and for each preferred term using MedDRA coding. A subject with multiple occurrences of an AE will be counted only once in the AE category.

Separate AE summaries will be presented by primary system organ class, preferred term, and maximum CTC grade. A subject with multiple CTC grades for an AE will be summarized under the maximum CTC grade recorded for the event. In the summaries presented by grade, all AEs will be pooled regardless of whether they are CTC gradable or not, i.e., regardless of whether the question “CTC AE” on the Adverse Events eCRF is answered ‘Yes’ or ‘No’.

The frequency of CTC grade 3 and 4 AEs will be summarized separately as well as summaries of all deaths and on-treatment deaths.

Any information collected (e.g., CTC grades, relatedness to study drug, action taken, etc.) will be listed as appropriate.

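### The final CSR compares AEs and AESIs between arms only as crude percentages over a window likely to be longer on everolimus, and time to first AESI is not re-summarised

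*SAP*

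**What the plan says.** SAP 1.2 states the safety objective as a comparison: "To characterize the safety and tolerability of everolimus and exemestane versus placebo and exemestane".

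**Measure.** SAP 2.8.1.3 says "AEs will be summarized by presenting the number and percentage of subjects having at least one AE", with each subject counted once per category. SAP 2.8.1.5 does the same for each AESI, giving by arm the "number and percentage of subjects with at least one event of the AESI occurring during on treatment period".

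**Window.** SAP 2.1.8 defines on-treatment as the interval "date of first administration of study treatment; date of last administration of study treatment + 30 days". SAP 2.1.5 takes the last administration to be "the last date when a non-zero dose of any component of study treatment was administered". Protocol 6.1.4 lets a patient who stops one drug continue the other until progression, so stopping everolimus alone need not close the window.

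**Stopping rule.** SAP 1.1: "Subjects will receive treatment until disease progression (assessed by RECIST 1.1), unacceptable toxicity, death", or discontinuation for another reason. Protocol 10.6 assumes median PFS of 4.1 v 6.6 months.

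**Time to event.** SAP 2.8.1.5: "Time to first occurrence of AESI by variable was provided in the primary CSR". It is not re-summarised in the final report, where only listings are updated. The AESI groupings come from a Case Retrieval Sheet that may change: "The most up-to-date version of the CRS will be used at the time of the analysis".

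Exposure duration is tabulated by arm (SAP 2.4.1 and 2.4.2) but is not linked to AE incidence. Neither document plans a rate per patient-time. The primary CSR and SAP Addendum 1 (cited for sample size) were not available to check.

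**The concern.** A crude percentage has no time denominator. If one arm is watched for longer, events that keep occurring through treatment accumulate there even when the drug does not cause them. Because the objective is comparative, readers will set the two columns side by side.

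This matters for later-onset or background events. It does not matter for events that occur early and with a large excess. Protocol 6.3.2.3 places most stomatitis in the first 8 weeks, when the difference in window length has little influence.

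Time to first AESI is the planned summary that would separate drug effect from time observed, and it stops at the primary cut-off. If the Case Retrieval Sheet has changed since then, the final percentages and the earlier time-to-first summary may also rest on different groupings.

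**Working it through.** **1. The plan's own figures.** 4.1 / 0.62 = 6.6 months. The 90% CI at 110 events is exp(ln 0.62 ± 1.645 × 2/√110) = 0.453 to 0.848, which matches the stated (0.45, 0.85).

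**2. Inputs.** Medians are 4.1 v 6.6 months (Protocol 10.6), 4.9 on everolimus as a low case (Table 10-1, HR 0.84) and 8.5 as a high case (the Asian subset of the earlier phase III trial, Protocol 1.2.1.2.2). The tail is t = 30/30.4375 = 0.986 months. Assumptions not in the documents: treatment time equals PFS time (exponential); the AE hazard h is constant and equal in both arms; illustrative placebo incidences of 5%, 10% and 20%.

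**3. Mean window** = median/ln 2 + t. Placebo: 4.1/0.693 + 0.986 = 6.9 months. Everolimus: 6.6/0.693 + 0.986 = 10.5 months. The ratio is 1.52 (1.17 at 4.9 months, 1.92 at 8.5).

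**4. Incidence** = 1 − exp(−h·t) × μ/(μ + h), with μ = ln 2/median.
- Placebo, μ = 0.1691: 10% requires h = 0.0159 per month, since 1 − 0.9845 × 0.9142 = 0.100.
- Everolimus, μ = 0.1050: 1 − 0.9845 × 0.8687 = 0.145.

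**5. Toxicity stops.** If a fraction f of everolimus patients stop both drugs before progression (none on placebo), μ becomes μ/(1 − f). For f = 0.20, μ = 0.1313 and incidence = 1 − 0.9845 × 0.8922 = 0.122. The windows are equal at f = 1 − 4.1/6.6 = 0.38.

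**6. Range.**

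| Everolimus median (months) | 5% on placebo becomes | 10% becomes | 20% becomes | 10%, with 20% stopping both drugs | f for equal windows |
|---|---|---|---|---|---|
| 4.9 | 5.8% | 11.5% | 22.6% | 9.7% | 0.16 |
| 6.6 | 7.4% | 14.5% | 27.6% | 12.2% | 0.38 |
| 8.5 | 9.2% | 17.6% | 32.5% | 14.8% | 0.52 |

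**7. Does the final update matter?** Take 80 per arm, uniform accrual over 18 months and a primary analysis at month 22 (Protocol 10.6), with treatment time again equal to PFS time and losses ignored. Patients still on treatment = (80/18) × (exp(−4μ) − exp(−22μ))/μ.
- Placebo: 4.444 × (0.5085 − 0.0243)/0.1691 ≈ 13.
- Everolimus: 4.444 × (0.6570 − 0.0992)/0.1050 ≈ 24.

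Further treatment time is that number divided by μ: about 75 v 225 patient-months. These are upper figures, because they ignore the final cut-off. They show that the windows diverge most after the primary analysis, which is the period that the existing time-to-first summary does not cover.

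**The case against.** The other side has several good points.

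- **The SAP follows the protocol.** Protocol 10.5.2.1 bases safety mainly on AE frequency, and 10.5.2.2 asks for the number and percentage of patients with an AESI by arm. A reader might infer a deviation or a broken rule; there is none. Safety is descriptive, with no test.
- **This is an update.** Protocol section 10 puts the main safety analysis at about 110 PFS events, and time to first AESI was reported then. That stands, but step 7 suggests that the added follow-up is the unbalanced part.
- **Exposure is tabulated by arm.** Readers can see unequal windows and approximate a simple rate, but cannot recover one censored at first event.
- **The size is unproven.** Longer exposure is inferred from PFS; no expected exposure is stated. The earlier trial's Table 1-2 does not validate the model. With its medians of 3.2 v 7.8 months, 15 of the 31 terms with a non-zero placebo rate fall below prediction (nausea: 47% predicted, 31% seen) and 16 above, including known everolimus effects.
- **Known AESI effects exceed any window effect.** The same model predicts 23% for stomatitis against 59% seen, and 4% for hyperglycemia against 14% seen. A reader might infer that the AESI excesses are artefacts of follow-up. The documents do not support that: the protocol lists many of these events as class effects of mTOR inhibitors.
- **Patient-time rates can mislead.** Suppose an event has equal hazard in both arms, but only in the first 8 weeks, with 10% on placebo and medians of 4.1 v 6.6 months. The crude percentages are 10.0% v 10.1%, yet the first-event rates are 0.0159 v 0.0106 per month, a ratio of 0.67 that wrongly favours everolimus. This is why such rates are not the main recommendation.

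**Conclusion.** The point holds as an optional, cheap improvement. The final CSR offers only crude percentages to compare AEs and AESIs between arms, over a window that the design implies, but does not guarantee, is longer on everolimus. For later-onset or background events the difference can partly reflect time observed. On the planned medians, 10% on placebo becomes up to about 14.5% with equal constant hazards and no toxicity stops, about 12% if 20% of everolimus patients stop both drugs early, and no different at 38%. The effect may be negligible.

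A reader might go further and conclude that the final tables will overstate everolimus harm. The documents do not establish that. It depends on actual exposure, on the pattern of toxicity stops and on when events occur, and none of these is given. The primary endpoint, the sample size and any error rate are untouched.

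**What to change.** In SAP 2.8.1.5, remove the statement that the time-to-first-AESI summary is not repeated. Plan instead a re-run by arm at the final cut-off, with patients without an event censored at last dose + 30 days, or at the data cut-off if earlier. Use the same Case Retrieval Sheet version as for the final percentages. Keep the crude tables, and add a footnote on window length if the exposure tables differ by arm.

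The cost is SAP wording and a few descriptive outputs from AE and dosing dates already collected, re-using a summary already produced for the primary CSR. The re-run needs no constant-hazard assumption, but the censoring does treat stopping treatment as unrelated to AE risk. It will be imprecise for rare AESIs.

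First-event rates per patient-month, with 90% CI, are optional only. They assume a constant hazard and can understate early-onset harm, so they should be read only beside the time-to-first summary. They are also wide: with 80 per arm and 8.0 v 11.6 expected events (10% v 14.5%), the 90% CI of a rate ratio spans a factor of exp(1.645 × √(1/8.0 + 1/11.6)) = 2.13 each way.

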2.8.2 Deaths

The number of deaths resulting from SAEs suspected to be related to study treatment and SAEs irrespective of study treatment relationship will be provided by SOC and PT. Summaries of all deaths and on-treatment deaths will be provided.

2.8.3 Laboratory data

Laboratory abnormalities that constitute an Adverse event in their own right (are considered clinically significant, induce clinical signs or symptoms, require concomitant therapy or require changes in study treatment), should be recorded on the Adverse Events CRF.

All laboratory values will be converted into SI units and the severity grade calculated using appropriate common toxicity criteria (CTCAE).

Laboratory abnormalities that meet the criteria for Adverse Events should be followed until they have returned to normal or an adequate explanation of the abnormality is found.

Laboratory abnormalities, that do not meet the definition of an adverse event, should not be reported as adverse events. A Grade 3 or 4 events (severe) as per CTCAE does not automatically indicate a SAE unless it meets the definition of serious adverse event.

A listing of laboratory values will be provided by laboratory parameter, subject, and treatment group. A separate listing will display notable laboratory abnormalities (i.e., newly occurring CTCAE grade 3 or 4 laboratory toxicities). The frequency of laboratory abnormalities will be displayed by parameter and treatment group.

Laboratory data summaries will include all laboratory assessments collected no later than 30 days after the last treatment/exposure date. All laboratory assessments will be listed and those collected later than 30 days after the last treatment/exposure date will be flagged in the listings.

Laboratory data will be classified (by Novartis biostatistics/SAS programming) into CTC grades according to the NCI Common Terminology Criteria for Adverse Events (CTCAE) v4.03. A severity grade of 0 will be assigned when the value is within normal limits. In the case when a local laboratory normal range overlaps into the higher (i.e., non-zero) CTC grade, the laboratory value will still be taken as within normal limits and assigned a CTC grade of zero.

The following rules will be applied:

- Conflict between normal range and grade definition: because many institutions have differences for normal ranges of metabolic laboratory and hematology values, the CTCAE often uses the terms 'Upper Limit of Normal (ULN)' and 'Lower Limit of Normal (LLN)' in lieu of actual numerical values. In some cases, an institution's LLN might be beyond the range specified for a grade. In this case, the institutional limits of normal should take precedence over the CTCAE values: the laboratory value will still be taken as within normal limits and assigned a CTC grade of zero.
- For the few parameters having comparison to baseline in CTCAE grading definition (Fibrinogen, INR, Hemoglobin, Creatinine), the highest grade will be retained. In other words, in the particular case when a value is grade x as per CTC grade definition based on threshold/ranges and grade x+1 when comparing to baseline, grade x+1 is retained.
- Grade values will be integers from 1 to 4. Grade 5 will only be used if the laboratory abnormality results in Death.
- For calcium, CTCAE grading is based on Corrected Calcium and not on Calcium. Corrected Calcium (CALC) will be calculated from Albumin and Calcium: Corrected Calcium (mg/dL) = Calcium (mg/dL) - 0.8 [Albumin (g/dL)-4].
- For creatinine clearance (CRCLCG parameter), no calculation of CTC grade will be done.

The following summaries will be produced for the laboratory data (by laboratory parameter and treatment):

- Number and percentage of subjects with worst post-baseline CTC grade (regardless of the baseline status). Each subject will be counted only for the worst grade observed post-baseline.
- Shift tables using CTC grades to compare baseline to the worst post-baseline value will be produced for hematology and biochemistry laboratory parameters with CTC grades.
- For laboratory parameters where CTC grades are not defined, shift tables to the worst post-baseline value will be produced using the low/normal/high classifications based on laboratory reference ranges.

The following listings will be produced for the laboratory data:

- Listing of subjects with laboratory values outside the laboratory reference ranges with values flagged to show the corresponding CTC grades and the classifications relative to the laboratory reference ranges.

- Listing of all laboratory data with values flagged to show the corresponding CTCAE grades and the classifications relative to the laboratory reference ranges.

Grading of laboratory values will be assigned programmatically as per NCI Common Terminology Criteria for Adverse Events (CTCAE) version 4.03. The calculation of CTCAE grades will be based on the observed laboratory values only, clinical assessments will not be taken into account.

CTCAE Grade 0 will be assigned for all non-missing values not graded as 1 or higher. Grade 5 will not be used.

For laboratory tests where grades are not defined by CTCAE v4.03, results will be categorized as low/normal/high based on laboratory normal ranges.

The following summaries will be generated separately for hematology, and biochemistry tests:

- Listing of all laboratory data with values flagged to show the corresponding CTCAE v4.03 grades if applicable and the classifications relative to the laboratory normal ranges
- Listing of notable laboratory abnormalities (i.e., newly occurring CTCAE grade 3 or 4 laboratory toxicities)

For laboratory tests where grades are defined by CTCAE v4.03.

- Worst post-baseline CTCAE grade (regardless of the baseline status). Each subject will be counted only once for the worst grade observed post-baseline.
- Shift tables using CTCAE grades to compare baseline to the worst on-treatment value
- For laboratory tests where grades are not defined by CTCAE v4.03, shift tables using the low/normal/high/ (low and high) classification to compare baseline to the worst on-treatment value.

